5.6. Medical History

General medical history will be collected at screening for general conditions (i.e., conditions not specific to the disease being studied). Medical history will be coded using the current Medical Dictionary for Regulatory Activities (MedDRA) dictionary.

General medical history will be summarized by system organ class (SOC) and preferred term (PT) and sorted by frequency in SOC and by decreasing frequency in PT for the Full Analysis Set.

A by-participant listing of general medical history will be provided by participant ID number in ascending order.

5.7. Prior and Concomitant Medications

Medications collected at screening and during the study will be coded using the current version of the World Health Organization (WHO) Drug dictionary.

5.7.1. Prior Medications/Radiation Therapies/Surgeries and Procedures

5.7.1.1. Prior Medications

Prior medications are defined as any medications taken before a participant took the first study drug.

Prior medications will be summarized by Anatomical Therapeutic Chemical (ATC) drug class Level 2 and preferred name using the number and percent of participants for each cohort.

A participant reporting the same medication more than once will be counted only once within each ATC drug class when calculating the number and percent of participants who received that medication. The summary will be ordered alphabetically by ATC medical class and then by preferred term in order of descending overall frequency within each ATC medical class. For drugs with the same frequency, sorting will be done alphabetically.

For the purposes of analysis, any medication with a start date prior to the first dosing date of study drug will be included in the prior medication summary regardless of when the stop date is. If a partial start date is entered the medication will be considered prior unless the month and year (if day is missing) or year (if day and month are missing) of the start date are after the first

dosing date. Medications with a completely missing start date will be included in the prior medication summary, unless otherwise specified.

Summaries will be based on the Safety Analysis Set. No formal statistical testing is planned.

5.7.1.2. Prior Radiation Therapies

Prior radiation therapy will be reported in a by-participant listing.

5.7.1.3. Prior Cancer Surgeries and Procedures

Prior cancer surgeries and procedures will be reported in a by-participant listing only.

5.7.2. Concomitant Medications

Concomitant medications are defined as medications taken while a participant took the study drug. Use of concomitant medications will be summarized by Anatomical Therapeutic Chemical (ATC) drug class Level 2 and preferred name using the number and percent of participants for each cohort. A participant reporting the same medication more than once within each ATC drug class will be counted only once when calculating the number and percent of participants who received that medication. The summary will be ordered alphabetically by ATC medical class and then by preferred term in descending overall frequency within each ATC medical class. For drugs with the same frequency, sorting will be done alphabetically.

For the purposes of analysis, any medications with a start date prior to or on the first dosing date of study drug and continued to be taken after the first dosing date or started on or after the first dosing date of study drug and continued until 30 days after the treatment discontinuation will be considered concomitant medications. Medications started and stopped on the same day as the first dosing date or 30 days after the treatment discontinuation will also be considered concomitant. Medications with a stop date prior to the date of first dosing date of study drug or a start date beyond 30 days after the treatment discontinuation will be excluded from the concomitant medication summary. If a partial stop date is entered, any medication with the month and year (if day is missing) or year (if day and month are missing) prior to the date of first study drug administration will be excluded from the concomitant medication summary. If a partial start date is entered, any medication with the month and year (if day is missing) or year (if day and month are missing) after the study drug stop date will be excluded from the concomitant medication summary. Medications with completely missing start and stop dates will be included in the concomitant medication summary, unless otherwise specified. Summaries will be based on the Safety Analysis Set. No formal statistical testing is planned.

All prior and concomitant medications (other than per-protocol study drugs) will be provided in a by-participant listing sorted by participant ID number and administration date in chronological order.

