### **5.2. Prior and Concomitant Medication Assessments**

Medications administered prior to the first dose of study drug will be recorded as prior medications, whereas medications initiated after administration of the first dose of study drug until 30 days after treatment discontinuation will be captured as concomitant medications. Medication information will be entered in the appropriate eCRF with information regarding dose, indication, route of administration, and dates of administration. Medications used for prophylaxis of anticipated study drug AEs as outlined in the protocol should be documented along with the rationale for prophylactic intent.

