Appendix 3. Missing Data/Partial Dates Imputation Rules

Missing Data Imputation for Missing Date of Birth

The following conventions will be used for the imputation of date of birth when it is partially missing or not collected:

In general, age collected at Day 1 (the randomization date) (in years) will be used for analyses and presented in listings. If age at Day 1 is not available for a participant, then age derived based on date of birth and the Day 1 visit date will be used instead. If an enrolled participant was not dosed with any study drug, the randomization date will be used instead of the Day 1 visit date.

For screen failures, the date the first informed consent was signed will be used for the age derivation.

Missing normal ranges for laboratory parameters

When either the lower limit of normal, the upper limit of normal or both are missing or are not machine readable, a standardized reference range will be used.

Missing Data Imputation for Missing Adverse Event/Concomitant Medication Start Date

1) Missing day only

- If the month and year of the AE/the concomitant medication are the same as the month and year of the first dose date, the first dose date day will be used.
- • If the month and year are before the month and year of the first dose date, the first day of the month will be assigned to the missing day.
- • If the month and year are after the month and year of the first dose date, the first day of the month will be assigned to the missing day.

2) Missing day and month

- If the year is the same as the year of the first dose date, the first dose date day and month will be used.
- If the year is prior to the year of the first dose date, December 31 will be assigned to the missing fields.
- If the year is after the year of the first dose date, January 1 will be assigned to the missing fields.

3) Missing day, month, and year

- Uncertain: unable to impute.

The imputed start date should be prior or equal to the end date of the AE or medication. If only month is missing, then it will be imputed in a similar way as scenario 2) above. If both year and month missing and day not missing, then it will be imputed in a similar way as scenario 3) above.

Missing Data Imputation for Missing Adverse Event/Concomitant Medication Stop Date

4) Missing day only

- The month and year are the same as the month and year of the first dose date: use the last date of the month.

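### SAP 5.7.2 applies a shorter concomitant-medication cut-off to partial start dates than to complete ones, so partially dated medications that may fall inside the 30-day window are left out of the summary

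*SAP*

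**What the plan says.** SAP 5.7.2 opens with a general definition: "Concomitant medications are defined as medications taken while a participant took the study drug". The operational rules that follow go further.

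- **Complete start date.** The section excludes a medication with "a start date beyond 30 days after the treatment discontinuation will be excluded from the concomitant medication summary". Day 30 itself counts: "Medications started and stopped on the same day as the first dosing date or 30 days after the treatment discontinuation will also be considered concomitant".
- **Partial start date.** A medication whose month and year (day missing) or year (day and month missing) falls "after the study drug stop date will be excluded from the concomitant medication summary".

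Protocol 5.2 uses the longer window: "medications initiated after administration of the first dose of study drug until 30 days after treatment discontinuation will be captured as concomitant medications".

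Two other parts of the SAP bear on this. Appendix 2 decides whether a partially dated adverse event is treatment-emergent by comparing its month and year (or year) with those of the date 30 days after last dose. Appendix 3, which covers start dates of adverse events and concomitant medications together, imputes a missing start day. When the known parts of the date "are after the month and year of the first dose date, the first day of the month will be assigned to the missing day".

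SAP Section 1 gives the SAP precedence where it differs from the protocol, so Protocol 5.2 does not override the partial-date sentence.

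**The concern.** Whether a medication begun shortly after the last dose enters the summary should depend on when it began. Under 5.7.2 it also depends on whether the site recorded the day. Two participants who start the same medicine on the same day after treatment can be classified differently because one record lacks a day.

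The loss runs in one direction. A partial start date in a later calendar month or year than the stop date is always excluded, including when the true start was inside the 30-day window. The concomitant-medication table would then undercount medicines started after treatment ended but within the period that the section and the protocol both intend to cover.

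**Working it through.** The plan states no figure to reproduce, so the check compares the rules and then uses calendar arithmetic.

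**1. The rules side by side**

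| Rule | Latest start that is kept | 30-day allowance |
|---|---|---|
| SAP 5.7.2, complete date | Day 30 after treatment discontinuation | Yes |
| SAP 5.7.2, partial date | Calendar month (or year) of the study drug stop date | No |
| Protocol 5.2 | 30 days after treatment discontinuation | Yes |
| SAP Appendix 2, partial adverse event date | Calendar month (or year) containing last dose + 30 days | Yes |

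**2. Assumption.** 5.7.2 uses both study drug stop date and treatment discontinuation and defines neither. For the arithmetic, both are set equal to the last dose date.

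**3. Month-only example.** Last dose 20 March 2022; the window ends 20 March + 30 days = 19 April 2022. A medication begun on 5 April is kept if fully dated and excluded if recorded as April 2022. Of the 30 days in April, 19 are inside the window and 11 are outside. Appendix 3 would impute 1 April, which is day 12.

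**4. Year-only example.** Last dose 15 December 2022; the window ends 14 January 2023. A start recorded as 2023 is excluded, although 14 of that year's 365 days are inside the window.

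**5. How much of the window is exposed.** For a last dose on day d of a 30-day month, d of the 30 window days fall in the next month. The mean of d/30 over d = 1 to 30 is (30 × 31 / 2) / (30 × 30) = 465/900 = 0.517.

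Counting over every last-dose date from 2020 to 2023 (1,461 dates, 1,461 × 30 = 43,830 window days):

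- Window days in a later calendar month than the last dose: 50.9%.
- Days of the next calendar month that lie inside the window: 50.2%. If starts are spread evenly over that month (an assumption), about half of the month-only exclusions in it would be wrong and half right.
- Last-dose dates for which the first of the next month is inside the window: 1,433/1,461 = 98.1%. The 28 exceptions are last doses on the 1st of a 31-day month (7 months × 4 years), where that day is day 31.
- Last-dose dates for which the year-only rule can wrongly exclude: 2 to 31 December, 30 × 4 = 120, and 120/1,461 = 8.2%.

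**6. What is unaffected.** Complete start dates inside the window are kept. Partial start dates in the same calendar month (or year) as the stop date are also kept.

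**The case against.** The best defence is that the section's opening definition covers only medicines taken while on study drug, and the partial-date cut-off fits that. This does not remove the conflict. The rules introduced for the purposes of analysis set a 30-day window and expressly count day 30, and Protocol 5.2 agrees. If the on-drug window were the intended one, the complete-date rule would be the one in error.

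A second defence is that 5.7.2 is the specific classification rule, while Appendix 3 is general imputation and does not say that an imputed date overrides it. This stands. A reader might infer that the SAP formally classifies one record both ways through Appendix 3, but the documents do not establish which rule is applied first. The firm conflict is within 5.7.2 and with Protocol 5.2. Nor would Appendix 3 imputation rescue every record, given the 28 exceptions.

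The objections on scale also stand. About 51% is a share of window days. It is not a share of medications or of participants in the table. 5.7.2 counts a participant once when the same medication is reported repeatedly, so a dropped repeat of something already used on treatment changes nothing. All prior and concomitant medications still appear in the by-participant listing.

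A reader might also infer that adverse event and medication summaries would fail to match because of this rule. The documents do not support that. SAP 7.1.5.1 ends the treatment-emergent window at 30 days after last dose or the day before subsequent anticancer therapy, whichever is earlier. The medication window runs from treatment discontinuation and has no such cut. The two can differ even with complete dates, and the SAP plans no analysis linking them.

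**Conclusion.** The partial-date cut-off in SAP 5.7.2 is wrong as written. It contradicts the complete-date rule in the same paragraph and Protocol 5.2, departs from the construction used for adverse events in Appendix 2, and is not reconciled anywhere.

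The reach is narrow: only records with a partial start date in a later calendar month or year than the stop date. It would be too strong to say that medications started in the month after last dose are dropped in general. Among partially dated records, about half of the 30-day window is exposed, if the three end-of-treatment dates coincide. The documents do not say how many start dates are partial, so the absolute effect cannot be calculated, but it is probably small. It touches one descriptive table and no efficacy endpoint or adverse event count.

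**What to change.** In SAP 5.7.2, exclude a partial start date only if its month and year (or year alone) is later than the month and year (or year) of the date 30 days after treatment discontinuation. Define one anchor date in that section and use it for both the complete-date and partial-date rules, since two undefined terms are used now. State also whether 5.7.2 or Appendix 3 governs the classification of partially dated records.

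The revised rule will keep some records that began after day 30: in the March example, a true start on any of 11 April days. The effect is larger for year-only dates. That is the inclusive choice the SAP already makes for adverse events, and because Protocol 5.2 captures these medications only to day 30, few later starts should be on file.

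The cost is a short wording change and one programming condition, with no new data.

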5.8. Non-protocol Specific Procedures/Surgeries

Non-protocol specific procedures/surgeries will be reported in a by-participant listing only.

6. EFFICACY ANALYSES

Efficacy analyses will be performed primarily based on the Full Analysis Set and may be also performed for selected endpoints based on the Efficacy Evaluable Analysis Set.

For the purposes of analysis for tumor response-based endpoints including ORR, DCR (disease control rate), CBR, BOR, DOR and PFS, documented progression refers to progression based on radiologic assessment as determined by the investigator or central review (BICR), not clinical progression.

Tumor response-based endpoints, including ORR, DCR, CBR, DOR, and PFS will be analyzed based on both investigator reviewed and BICR results.

6.1. Primary Efficacy Endpoint

6.1.1. Definition of the Primary Efficacy Endpoint

The primary efficacy endpoint of this study is objective response rate (ORR) defined as the proportion of all participants with measurable disease at baseline who achieve complete response (CR) or partial response (PR) that is confirmed at least 4 weeks after initial documentation of response per RECIST v1.1, as determined by investigator. Tumor response assessments after the date of participants receiving subsequent anticancer therapy will be excluded from the analysis. The response definition of each response category is based on RECIST v1.1.

6.1.2. Statistical Hypothesis for the Primary Efficacy Endpoint

There is no statistical hypothesis for the POC stage.

6.1.3. Analysis of the Primary Efficacy Endpoint

ORR will be summarized for the Full Analysis Set along with the number and percent of participants in each response category.

The 2-sided 95% exact confidence interval (CI) of ORR based on Clopper-Pearson method [{Clopper 1934}](#) will be provided for each cohort.

Additionally, a plot of target-lesion tumor burden over visit (spider plot) will be provided for the Full Analysis Set, where the tumor burden is defined as the percent change from baseline in total sum of target lesion diameters. A plot of maximum tumor burden reduction (waterfall plot) and a table of maximum tumor burden reduction will be provided for the Full Analysis Set, where maximum tumor burden reduction is defined as the best percent change from baseline in total sum of target lesion diameters. A plot of participants' overall response assessment over visit (swimmer plot) will be provided for the Full Analysis Set.

6.1.4. Sensitivity Analysis of the Primary Efficacy Endpoint

A sensitivity analysis of the primary endpoint may be performed based on the Efficacy Evaluable Analysis Set.

6.2. Secondary Efficacy Endpoints

6.2.1. Definition of Secondary Efficacy Endpoints

Clinical Benefit Rate (CBR)

CBR is defined as confirmed CR + PR + SD for at least 6 months, according to RECIST v1.1 by the investigator or BICR. For participants who have best response of SD, the duration of SD is defined as the time from the date of first dose of study drug to the first documentation of PD or death due to any cause.

Disease Control Rate (DCR)

Disease control rate (DCR) is defined as the proportion of participants who achieve a confirmed CR, PR, or stable disease (SD) as assessed by the investigator or BICR per RECIST v1.1.

Time to Response (TTR)

Time to onset of objective response (CR or PR) will be calculated for objective responders as the time from the date of first dose of study drug to the first documentation of response according to RECIST v1.1.

Time-to-response (TTR) by RECIST v1.1 will be summarized based only on participants who achieved a best overall response of confirmed CR or PR. TTR will be summarized by descriptive statistics, and by the number and percent of responders whose TTR is within 3 months, 6 months, and 12 months.

Duration of Response (DOR)

Duration of response (DOR) is defined as the time interval from the date of first response (CR or PR) to the earlier of the first documentation of definitive disease progression or death from any cause as assessed by the investigator per RECIST v1.1, which occurs first. The analyses of DOR will be based on the participants in the Full Analysis Set who achieve a confirmed CR or PR. The censoring rules for DOR are specified in [Table 1](#).

DOR in months will be derived as (date of event/censoring – date of first response [CR or PR] + 1) / 30.4375.

Table 1. Censoring Rules for DOR

Case	Outcome	Date of Event/Censoring
Continued scheduled response assessments until objective PD or death		
PD or death documented after ≤ 1 missed disease assessments, and before other anti-cancer therapy, if any	Event	PD or Death date, whichever occurs first
PD or death immediately after ≥ 2 consecutive missed disease assessments, or after other anti-cancer therapy, if any	Censored	Date of last adequate tumor assessment prior to the earlier date of ≥ 2 consecutive missed disease assessment and other anti-cancer therapy, if any
Continued scheduled response assessments without objective PD or death		
Other anti-cancer treatment is initiated	Censored	Date of last adequate tumor assessment before starting other anti-cancer treatment
Other anti-cancer treatment is not initiated	Censored	Date of last adequate tumor assessment

Progression Free Survival (PFS)

PFS will be defined as the time from the date of first dose of study drug to the date of first documentation of disease progression by investigator assessment or BICR based on RECIST v1.1 or death due to any cause, whichever comes first. The censoring rules for PFS are specified in [Table 2](#).

Table 2. Censoring Rules for PFS

Case	Outcome	Date of Event/Censoring
No adequate response assessment after the first dose		
No baseline tumor assessment or alive	Censored	First dose date
Died prior to second scheduled disease assessment without initiation of other anti-cancer therapy	Event	Death date
Died immediately after ≥ 2 consecutive missed assessments or new anti-cancer therapy, if any	Censored	First dose Date
Continued scheduled response assessments until objective PD or death		
PD or death documented after ≤ 1 missed disease assessments, and before other anti-cancer therapy, if any	Event	PD or Death date, whichever occurs first
PD or death immediately after ≥ 2 consecutive missed disease assessments, or after other anti-cancer therapy, if any	Censored	Date of last adequate tumor assessment prior to the earlier date of ≥ 2 consecutive missed disease assessment and other anti-cancer therapy, if any
Continued scheduled response assessments without objective PD or death		
Other anticancer treatment is initiated	Censored	Date of last adequate tumor assessment before starting other anti-cancer treatment
Other anticancer treatment is not initiated	Censored	Date of last adequate response assessment

Overall Survival (OS)

OS will be measured from the date of first dose of study drug to death from any cause. Participants not known to have died are censored on the date they were last known to be alive.

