#### **4.4. End of Treatment Visit**

The End of Treatment (EOT) Visit should be conducted within 30 days after the decision has been made to discontinue treatment. If this is scheduled for 30 days ( $\pm$  14 days) after the last dose, the results from these assessments may also be used for the 30-Day Safety Follow-up Visit. Subjects who discontinue treatment because of toxicity will continue with radiologic response assessments at the protocol-required schedule, until PD or initiation of new therapy with capture of radiologic evidence of PD if clinically feasible. The reason for treatment discontinuation will be documented and any treatment-related AEs or clinically significant abnormal laboratory values at that time will be followed until resolution or stabilization.

- Complete physical examination including weight.
- Blood samples for:

- CBC with differential.
- Serum chemistry panel and liver function tests, glucose, creatinine, BUN, total bilirubin, AST, ALT, alkaline phosphatase, serum albumin, sodium, potassium, calcium, chloride, bicarbonate, magnesium, and phosphorus.
- Urine pregnancy test.
- Tumor assessment: CT or MRI scan with IV contrast as appropriate (chest, abdomen, pelvis, and other regions of known/suspected involvement), unless known anaphylaxis to contrast or medically contraindicated as described in Section 9. If imaging was obtained within 2 weeks of the EOT Visit, imaging does not need to be repeated.
- Blood collection for PK and ADA serum samples.
- Blood collection for biomarker samples.
- Record AEs.
- Concomitant medications.
- **CCI**

For subjects continuing treatment following implementation of PA5, EOT assessments will be performed according to [Table 3](#).

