## 9. ASSESSMENT OF EFFICACY

CT or MRI scans with IV contrast of the chest, abdomen, pelvis, and any other involved disease sites (including brain MRI if appropriate) are to be obtained in all subjects (unless known anaphylaxis to contrast and/or medically contraindicated). If the use of IV contrast is medically contraindicated for a subject, 1 of the following options may be used (listed in order of preference): CT without contrast, MRI without contrast, or attempt to desensitize the subject with steroids. For each subject, the same imaging technique should be used throughout the study for tumor assessment. If a subject had brain lesions at study entry, brain MRI will be needed at all assessments. The timing of imaging is based on calendar time from the date of C1D1. Scans will be performed for all subjects at baseline and every 6 weeks for the first 6 months after C1D1 and then every 9 weeks thereafter until the occurrence of radiologic PD, as per RECIST 1.1, requiring discontinuation of treatment. Dose delays and cycle delays should not result in delays in the timing of imaging. For subjects with evidence of CR or PR, a confirmatory scan must be obtained at least 4 to 6 weeks after initial documentation of response CR or PR. Scans will be transferred to a central reader for collection and analysis by blinded independent central review (BICR).

Target and non-target lesions must be determined by the clinical site at baseline. Subjects who discontinue from treatment because of toxicity or clinical progression will continue to obtain radiologic response assessments at the protocol-required schedule until radiologic evidence of PD or initiation of new therapy, if clinically feasible. Additional CT or MRI studies may be performed at the discretion of the subject's treating physician to assess disease status, as medically indicated. Tumor response and progression will be determined using RECIST 1.1. For subjects who continue treatment despite radiologic evidence of PD as defined in Section 4.3.1, the subject will remain in the study and continue to be monitored according to the protocol required schedule of assessments ([Table 2](#)). The results of all imaging including those not specified as protocol assessments will be recorded on the eCRF.

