6.2.2. Analysis Methods for Secondary Efficacy Endpoints

Clinical Benefit Rate (CBR) and Disease Control Rate (DCR)

CBR and DCR will be summarized for the Full Analysis Set along with the number and percent of participants in each response category. 95% confidence intervals of CBR and DCR will be calculated using the Clopper Pearson method [{Clopper 1934}](#). An additional sensitivity analysis of CBR and DCR may be performed based on the Efficacy Evaluable Analysis Set.

Duration of Response (DOR)

The analysis of duration of response (DOR) will be performed using the Kaplan-Meier method for the responding participants in the Full Analysis Set. Median, Q1, and Q3 of the DOR will be provided along with the corresponding 95% CI for each cohort. Kaplan-Meier curves will be provided by cohort.

The follow-up time for DOR, defined as the time from the first documentation of response according to RECIST v1.1. to the date of death or the last known alive date if participants are not dead, will be summarized descriptively.

Progression Free Survival (PFS)

A Kaplan-Meier analysis will be performed for the PFS data using the Full Analysis Set. Median PFS will be derived and 95% confidence will be calculated based on Brookmeyer and Crowley method [{Brookmeyer 1982}](#). The milestone PFS rate at 3 months, 6 months, 12 months, 18 months will be derived from the KM curve.

Overall Survival (OS)

A Kaplan-Meier analysis will be performed for the OS data using the Full Analysis Set. Median OS will be derived, and 95% confidence will be calculated based on Brookmeyer and Crowley method [{Brookmeyer 1982}](#). The milestone OS rate at 6 months, 12 months, and 24 months will be derived from the KM curve.

The follow-up time for OS, defined as the time from the date of first dose of study drug to the date of death or the last known alive date if participants are not dead, will be summarized descriptively.

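### CBR lets stable disease run to death with no censoring, so survival after new therapy or two missed scans can count as six months of SD while PFS is censored much earlier

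*SAP*

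**What the plan says.** SAP 6.2.1 defines CBR as confirmed CR or PR, or SD lasting at least 6 months, by Investigator or BICR. Where SD is the best outcome, its length is set as follows: "duration of SD is defined as the time from the date of first dose of study drug to the first documentation of PD or death", from any cause. SAP 6 states, for CBR among other endpoints, that "documented progression refers to progression based on radiologic assessment as determined by the investigator or central review (BICR), not clinical progression".

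Censoring is set out in two tables in SAP 6.2.1, Table 1 for DOR and Table 2 for PFS. Under Table 2, PD or death immediately after two or more "consecutive missed disease assessments, or after other anti-cancer therapy, if any", is censored at the last adequate scan before the gap or the new therapy. PD or death after at most one of the "missed disease assessments, and before other anti-cancer therapy, if any", is an event. Neither table is assigned to CBR, and the CBR analysis text in SAP 6.2.2 adds only the analysis set and a Clopper-Pearson interval.

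The nearest related rule sits in the ORR definition (SAP 6.1.1): "Tumor response assessments after the date of participants receiving subsequent anticancer therapy will be excluded from the analysis".

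On imaging, Protocol 9 has participants who stop treatment for toxicity or clinical progression continue "radiologic response assessments at the protocol-required schedule until radiologic evidence of PD or initiation of new therapy, if clinically feasible". Protocol 4.4 requires a scan at the end-of-treatment (EOT) visit, but "If imaging was obtained within 2 weeks of the EOT Visit, imaging does not need to be repeated". Survival contact continued every 12 weeks (Protocol 4.7) until Amendment 5 (PA5).

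**The concern.** The SD rule starts and stops on the same events as PFS but without the PFS censoring. Once imaging has stopped, the only event left to end SD may be death, and deaths are still captured through survival follow-up. Time alive after the last scan, including time on a later anti-cancer therapy, can then be credited to the study drug as stable disease. For the same participant and the same assessor, PFS would be censored at the last adequate scan.

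The ORR rule on subsequent therapy does not close the gap. It is not stated for CBR, and it concerns tumor assessments rather than deaths or missed scans. If carried over to CBR, it would discard a PD seen after new therapy and let SD run on to death.

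BICR offers a further route. Treatment decisions follow the Investigator's reading, so if the Investigator calls PD and BICR reads SD, scanning may stop and new therapy may start with no BICR progression on record.

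In all these routes the error can only raise CBR, which is a secondary endpoint by both assessors. The SAP revision table gives regulatory, conference and publication use as the reason for this analysis.

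**Working it through.** The plan states no CBR figure to reproduce, so the check applies both rules to the same timelines.

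**Inputs**
- Month length: 30.4375 days. The SAP states this for DOR and treatment duration; it is assumed here for SD.
- Threshold: 6 × 30.4375 = 182.6 days, so day 183.
- Scans (Protocol 9): every 6 weeks for 6 months, then every 9 weeks, each ±7 days. This gives weeks 6, 12, 18, 24 and 33. It is read from the text because the pre-PA5 schedule table is redacted.
- Minimum for SD (Protocol Appendix 17.4): 6 to 8 weeks, or 42 to 56 days. A week-12 scan (days 77–91) clears it.
- Planned cohort sizes (SAP 1.3): 30, 35 and 40.

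**Timelines** (months = days after first dose / 30.4375)

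| Timeline | SD duration, CBR rule | PFS, Table 2 |
|---|---|---|
| 1. SD on day 84; EOT visit by day 84 + 14 = 98, no repeat scan; other therapy; no documented PD; death on day 240 | 240/30.4375 = 7.89: counts | Censored day 84: 2.76 |
| 1b. As 1, but a later EOT scan on day 110 shows SD before other therapy starts | 7.89: counts | Censored day 110: 3.61 |
| 2. SD on day 84; weeks 18 (day 126) and 24 (day 168) missed; no other therapy; death on day 200 | 200/30.4375 = 6.57: counts | Censored day 84: 2.76 |

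If the EOT scan in timeline 1 showed PD, SD would end there and the participant would not count. Adding one day, as the SAP's DOR formula does, moves the threshold from day 183 to day 182 and changes no classification above.

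**Weight of one participant:** 1/30 = 3.3 points; 1/35 = 2.9; 1/40 = 2.5.

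**A related gap.** SD with neither PD nor death and a last scan before day 183 has no stated classification. It can arise from withdrawal, loss to follow-up, missed scans or new therapy. PA5 is not a likely source: from the estimated last enrolment (30 May 2023) to its date (17 December 2024) is 567 days, and 567/30.4375 = 18.6 months. This relies on an estimated enrolment date.

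**Where the scans fall relative to 6 months.** Week 24 is day 168 (window 161–175), or 5.52 months (5.29–5.75), which is short of the threshold. Week 33 is day 231 (window 224–238), or 7.59 months (7.36–7.82). No scheduled scan falls between them.

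**The case against.** The strongest reply is that this is a missing cross-reference, not a competing rule. The SD sentence nearly repeats the PFS definition, which also contains no censoring until it points to Table 2. Because SD without PD or death has no end date, a programmer needs a convention, and Table 2 is the obvious one. The phrase tying 6-month SD to RECIST could also be read as requiring a scan at 6 months. That may well be the intention, but the SAP does not say so. It gives an explicit duration rule that requires no such scan and, followed as written, produces the results above.

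The protocol also has safeguards. All imaging is to be recorded, including unscheduled scans (Protocol 9). Follow-up for progression continues after treatment stops (4.6). Every effort is to be made to document objective progression (10.2.2.6, Appendix 17.4). The EOT scan can narrow the missed-scan route as well as the new-therapy route. These make the cases rarer without removing them: a PD first recorded after new therapy and beyond day 183 would still credit time on that therapy as SD.

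On size, one participant moves CBR by 2.5 to 3.3 points, against planned ORR half-widths of 13.4 to 15.5 points at the same sample sizes. The POC stage has no hypothesis. This stands, and it is why the point is minor.

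Finally, treating early-censored SD as non-benefit leans the other way. A participant with SD at week 24 who starts new therapy on day 190 would not count, while one with SD at week 24 and PD at week 33 would. This also stands, and it is the reason for the sensitivity analysis.

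**Conclusion.** The concern holds. As written, CBR can count a death after new therapy, or after two or more missed scans, as at least 6 months of SD: 7.9 or 6.6 months in the examples, where PFS for the same participant is censored at 2.8. The number of participants affected cannot be estimated from the documents, and the EOT scan reduces it, so no total shift in CBR is claimed.

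The conclusion rests on the literal text of SAP 6 and 6.2.1, the SAP's month conversion carried over to SD, and the scan schedule as described in Protocol 9. CBR is descriptive. ORR, DOR, PFS, OS and the expansion trigger, which is based on CR and PR, are unaffected. Severity is minor.

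**What to change.** In SAP 6.2.1:
- End SD duration at the Table 2 PFS event or censoring date, derived separately for Investigator and BICR.
- Count SD as clinical benefit only if that date is at least 6 months (182.6 days) after first dose, and otherwise as non-benefit. This also settles SD with neither PD nor death.
- Add a sensitivity analysis in which SD at the week-24 scan, within days 161–175, counts as 6 months.

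This is a short change to a definition and reuses dates already derived for PFS. The cost is that CBR may fall, by an amount the documents do not allow to be estimated: censored SD would need an adequate scan on or after day 183, and the first scheduled one is week 33.

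Two limits should be stated with the change. First, it aligns participant-level dates only. SAP 6.2.2 says "The milestone PFS rate at 3 months, 6 months, 12 months, 18 months will be derived from the KM curve", and CBR will still differ from the 6-month rate because censored SD counts as non-benefit. Second, a death after a single missed scan without new therapy (for example SD on day 126, week 24 missed, death on day 200) still ends SD at the death date, as it does in PFS.
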